A recent systematic review and meta-analysis published in the Cochrane Library concluded there is no difference in morbidity or mortality between restrictive and liberal transfusion strategies. However, these trials are often confounded by transfusions administered pre-randomization, a lack of comparable transfusion dosing regimens between studies, and at times small differences in actual mean pre-transfusion haemoglobin levels between control and intervention arms. In addition, these randomized controlled trials still leave many important questions unanswered. For example, are haemoglobin thresholds lower than 70 g/L just as effective as haemoglobin levels higher than 70 g/L? Some have suggested lower haemoglobin thresholds may be just as effective. Interestingly, lower thresholds are already applied in clinical practice in challenging patient populations.

Other studies have investigated mortality in patients with very low haemoglobin levels who do not receive red blood cell transfusions. These studies found that each 10 g/L decrease in haemoglobin below 80 g/L was associated with a 1.8 to 2.5 times increased odds of mortality, with sharper increases in mortality observed when the haemoglobin fell below 50 g/L. However, these studies do not address what effect red blood cell transfusion would have on outcomes at various nadir or pre-transfusion haemoglobin levels.

Additionally, while many studies have investigated the effect of anaemia on outcomes independent of red blood cell transfusion, and the effect of red blood cell transfusion on outcomes independent of anaemia, very few investigate if and how these two independent risk factors interact with each other.

The aim of this study is to determine what relationship red blood cell transfusion has with mortality and length of stay at various levels of nadir haemoglobin. To achieve this objective a retrospective observational study will be conducted, involving three hospitals from Western Australia. The study will include all elective and emergency surgical admissions over a 9 year period (July 2008 – June 2017).

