### **4. Benefits**

This study proposal includes important strengths. First, it involves admissions over a 9 year period from three hospitals across the largest surgical specialties responsible for transfusion and therefore will provide a large sample size for analyses. Second, this study will be conducted in a health service with low mean pre-transfusion haemoglobin thresholds, indicating there are likely more transfused and non-transfused patients at comparatively lower nadir haemoglobin levels available for analyses. Given these two important characteristics this study will likely have more power to detect differences in outcomes between transfused and non-transfused patients at lower levels of haemoglobin than previously reported.

Third, while some studies have investigated the impact of nadir haemoglobin and transfusion on outcomes, they focused on specific patient groups. This study will focus on the major surgical groups responsible for the majority of red blood cell transfusion and thus will increase the generalizability of results to other tertiary hospitals.

Thus the results of this proposed study will make an important contribution to the current body of literature and may guide future decisions on what transfusion thresholds researchers select for randomized controlled trials, or whether these randomized trials are even asking the correct research questions.

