## **6.2. Description of data gathering methods, including definitions of variables.**

The majority of data needed for this project will be sourced from the *Western Australian Patient Blood Management System*. The advantages of sourcing the majority of data from one system include consistent data collection processes and classification of variables.

The exposure variables of interest are degree of anaemia and red blood cell transfusion. Anaemia will be defined using the nadir haemoglobin result during admission for those not transfused and the pre-transfusion haemoglobin result in patients transfused, as described previously. The pre-transfusion haemoglobin will be the closest level measured prior to the first red blood cell transfusion administered. Fridges are available for storing blood in theatres and because of this the timing of red blood cell transfusion in the operating room is unknown. Therefore for patients transfused in the operating room the nadir haemoglobin result will be used as a surrogate for the pre-transfusion haemoglobin result. Haemoglobin levels will be grouped into the following categories: below 50 g/L, 50-59 g/L, 60-69 g/L, 70-79 g/L, 80-89 g/L, 90-99 g/L, 100 g/L or over. These cutoffs were selected after reviewing similar studies.

The main outcome variables of interest are mortality and hospital length of stay of current admission. For the mortality analysis, both in-hospital and 30-day all-cause mortality will be assessed. In-hospital and 30-day mortality will be calculated from date of death recorded in hospital patient admission systems (TOPAS/WebPas). Potential confounders collected will include age at admission, sex, hospital, discharge year, admission type (emergency or elective), clinical specialty, and patient comorbidities.

Patient comorbidities will be assigned a score based on the Charlson Comorbidity Index derived from ICD-10 codes for the comorbidities identified. To ensure the Charlson score represents patient comorbidities on admission, hospital-acquired complications will be excluded from the calculation.

Other data items to be collected include admission date, discharge date, discharge specialty, diagnosis related group, hours in ICU, presence of a red blood cell transfusion (yes/no), had a massive transfusion (yes/no), and number of red blood cell units transfused.

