### **6.4. Statistical methods.**

Exposure and outcome variables will initially be described by univariate and bivariate statistics, the latter using the chi-squared test for categorical variables and independent samples t-test for continuous variables. Logistic regression models will be applied to test the relationship that both red blood cell transfusion and nadir haemoglobin levels have with in-hospital mortality and 30-day mortality. A zero-truncated negative binomial regression model will be applied to the length of stay outcome. All regression models will adjust for the same potential confounders. A robust variance adjustment will be applied to the regression models to account for any potential correlation between multiple admissions for the same patient.

For this analysis we are also interested in whether the presence of a red blood cell transfusion modifies the effect of nadir haemoglobin on in-hospital mortality, 30-day mortality and length of stay. To test any effect modification on outcome an interaction term between nadir haemoglobin level and red blood cell transfusion will be added to the multivariable logistic regression models. Only significant interactions (defined as p-values <0.05) will be reported, with calculated odds ratios for interaction terms presented.

In addition, Kaplan-Meier curves and Cox proportional hazards models will be plotted to show time to death in patients transfused red blood cells when compared to patients not transfused red blood cells across the various nadir haemoglobin levels.

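### Haemoglobin is adjusted for only in seven bands, two of them open-ended, which leaves some residual confounding that can pass for transfusion harm

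*Protocol*

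**What the plan says.** Section 6.2 of the protocol defines the haemoglobin exposure in seven groups: "Haemoglobin levels will be grouped into the following categories: below 50 g/L, 50-59 g/L, 60-69 g/L, 70-79 g/L", then "80-89 g/L, 90-99 g/L, 100 g/L or over". Five are closed 10 g/L bands. The lowest and the highest are open-ended. The only reason given for the cut-offs is their use in similar studies.

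The value being grouped depends on exposure. It is defined "using the nadir haemoglobin result during admission for those not transfused and the pre-transfusion haemoglobin result in patients transfused", except that "for patients transfused in the operating room the nadir haemoglobin result will be used as a surrogate".

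Section 6.4 uses logistic regression to "test the relationship that both red blood cell transfusion and nadir haemoglobin levels have with in-hospital mortality and 30-day mortality", and for effect modification "an interaction term between nadir haemoglobin level and red blood cell transfusion will be added to the multivariable logistic regression models". All regression models share one set of confounders. The list in section 6.2 covers age, sex, hospital, year, admission type, specialty and comorbidity. No continuous haemoglobin term appears in that list or in the model description.

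On prognosis, the Synopsis reports that in patients not transfused "each 10 g/L decrease in haemoglobin below 80 g/L was associated with a 1.8 to 2.5 times increased odds of mortality", with a sharper rise below 50 g/L that it does not quantify. Section 4 expects "more power to detect differences in outcomes between transfused and non-transfused patients at lower levels of haemoglobin".

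**The concern.** The Synopsis itself says that red cells are commonly given to correct low haemoglobin. If the chance of transfusion rises as haemoglobin falls, it does so inside a band as well as between bands. A transfused patient in the 70-79 g/L band is then likelier to be near 70 than near 79. If mortality also rises as haemoglobin falls within the band, the transfused group carries a worse prognosis that the band indicator cannot remove. The model attributes the remainder to transfusion.

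The wider the band, the more room there is for this, so the two open-ended bands deserve most attention. Below 50 g/L matters particularly, because that is where the protocol reports the sharpest mortality increase. The comparison affected is the one the study exists to make (objective 1). Since the bias is unequal across bands, the interaction (objective 2) is affected too. With 60,000 to 70,000 admissions, a modest bias in well-filled bands need not be hidden by sampling error.

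**Working it through.** The protocol gives no haemoglobin distribution, transfusion probability or power calculation, so there is no figure of its own to reproduce. The check asks what odds ratio (OR) would appear if transfusion had no effect at all.

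**Inputs from the protocol.** The seven bands (section 6.2); mortality OR per 10 g/L fall, g = 1.8 to 2.5, below 80 g/L only (Synopsis); 60,000 to 70,000 admissions (section 6.5), taken as 65,000.

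**Assumptions, not in the protocol.** Haemoglobin normal, with mean 100 and SD 18 or mean 105 and SD 20 g/L; transfusion probability logistic in haemoglobin, 50% at 72 or 75 g/L, slope 0.15 or 0.25 per g/L.

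**Formulas.** Within each band, gap d = mean haemoglobin of non-transfused minus mean of transfused, by numerical integration. Spurious OR ≈ g^(d/10).

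| Band (g/L) | Gap d (g/L) | OR at g = 1.8 | OR at g = 2.5 |
|---|---|---|---|
| below 50 | 2.26-3.44 | 1.14-1.22 | 1.23-1.37 |
| 50-59 | 1.01-1.56 | 1.06-1.10 | 1.10-1.15 |
| 60-69 | 1.09-1.70 | 1.07-1.11 | 1.11-1.17 |
| 70-79 | 1.17-1.92 | 1.07-1.12 | 1.11-1.19 |
| 80-99 (two bands) | 1.21-1.96 | no gradient given | no gradient given |
| 100 or over | 8.9-14.0 | no gradient given | no gradient given |

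For example, the upper value for 70-79 g/L is 2.5^(1.92/10) = 1.19. The closed bands below 80 g/L therefore give about 1.05 to 1.20, and the band below 50 g/L about 1.15 to 1.4. The latter does not include the sharper gradient the protocol mentions there. Its upper end is approximate: averaging risk over the band, with mortality odds of 0.5% at 80 g/L, gives 1.17 to 1.47.

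**From 80 g/L upwards.** With no gradient the spurious OR is 1.00. With an assumed 1.3 per 10 g/L it reaches 1.3^(1.96/10) = 1.05 at 80-99 g/L. At 100 g/L or over, assumed gradients of 1.1 to 1.3 give 1.1^0.89 = 1.09 to 1.3^1.4 = 1.44.

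**Interaction.** If there is no gradient at 80-89 g/L, the apparent ratio of transfusion ORs between 60-69 and 80-89 g/L is 1.07 to 1.17, although transfusion does nothing in either band.

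**Other assumptions.**
- Mean 105 or 112, SD 18, midpoint 75 g/L and transfusion OR of 3, 6 or 10 per 10 g/L fall: 1.05 to 1.18 in closed bands below 80 g/L, 1.10 to 1.32 below 50 g/L, and a Mantel-Haenszel OR over all bands of 1.01 to 1.15.
- Mean 100, SD 18, midpoint 65 g/L and slope 0.08: gaps fall to 0.59-0.64 g/L in the closed bands below 80 g/L, so 1.8^0.059 = 1.04 to 2.5^0.064 = 1.06. Below 50 g/L the gap is 1.56 g/L, so 1.10 to 1.15.

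**Cell counts per 65,000 admissions.** Under the main assumptions there are 0 to 4 non-transfused patients below 50 g/L and 6 to 61 at 50-59 g/L. With midpoint 65 g/L and slope 0.08 these become about 30 and 224. The band at 100 g/L or over holds about 5 to 200 transfused patients against 32,000 to 39,000 non-transfused.

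**The case against.** The strongest reply is that bands suit a question posed at various levels of haemoglobin, that the cut-offs have precedent, and that a statistical analysis plan, not shown here, could add a continuous term. This partly stands. Bands are a reasonable way to present results, and the protocol does not forbid a finer adjustment. But the bands and the models are both fixed in the protocol, and band-only adjustment is the natural reading of sections 6.2 and 6.4.

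Four stronger readings are tempting, and the document does not support them.

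- *The exact value is discarded.* Section 6.2 says only that levels will be grouped.
- *Every band is biased, always against transfusion.* That transfused patients sit lower within a band is an inference, not a reported fact. The cited gradient stops at 80 g/L. The recorded value is also defined differently by transfusion status, which this calculation ignores, so a uniform direction is not shown.
- *The top band is the main problem.* Its gap is the largest, but the documents give no gradient there. With as few as 5 transfused patients under some of the assumptions, sampling error could swamp any bias.
- *The lowest non-transfused cells will be nearly empty.* The counts move several-fold with the assumed midpoint and slope. Section 4 describes a health service that transfuses at low levels, which favours fuller cells.

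**Conclusion.** The point holds in a limited form. Followed as written, the plan leaves residual confounding towards apparent transfusion harm wherever transfusion probability and mortality both change with haemoglobin inside a band. Under the main assumptions it is modest in the closed bands below 80 g/L (spurious OR about 1.05 to 1.20) and larger below 50 g/L (about 1.15 to 1.4). A flatter relation between haemoglobin and transfusion lowers both. From 80 g/L upwards it cannot be determined from the document and may be nil. It cannot by itself create a large transfusion effect, but it can shift a small one and distort the interaction. Length of stay and time to death share the banding, but the protocol gives no gradient from which to size their bias. Sparse non-transfused cells below 60 g/L are possible, not established. The change is worth making because the bias is avoidable at almost no cost.

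**What to change.** Keep the seven bands for tables and descriptive results. In sections 6.2 and 6.4, state that the exact haemoglobin value enters all regression models in one of two ways:

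- preferably, as a restricted cubic spline interacting with transfusion, with a joint test of the interaction terms and the transfusion effect with 95% CI reported at fixed values such as 55, 65, 75, 85 and 95 g/L; or
- at least, as a continuous within-band covariate in the band models, ideally with band-specific slopes, since the cited gradient is not constant.

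No new data are needed, because the bands are built from the laboratory result. Seven bands with interaction use 6 + 6 = 12 terms beside the transfusion main effect. A four-knot spline with interaction uses 3 + 3 = 6. A within-band covariate adds 1 term with a common slope, or 7 with band-specific slopes. That is small against 60,000 to 70,000 admissions. The other cost is a slightly less simple presentation.

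The spline also eases the problem of sparse low bands by borrowing from neighbouring values, though intervals there will stay wide. Splitting the top band, merging the lowest two, or using Firth regression are optional. None of this removes the separate difference in how haemoglobin is defined for transfused and non-transfused patients.

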## **5. Literature Review**

Rhode and colleagues pooled the results of 18 trials investigating what effect restrictive pre-transfusion haemoglobin thresholds have on hospital acquired infections. They found patients assigned to restrictive transfusion thresholds had a significantly lower risk of infection when compared to patients assigned to liberal transfusion thresholds (risk ratio 0.82, 95% CI 0.72 to 0.95). This significant risk reduction remained unchanged in a sub group analysis of trials using leukocyte reduced red blood cells.

Curley and colleagues conducted a systematic review and meta-analysis of randomized controlled trials comparing restrictive to liberal transfusion haemoglobin thresholds in patients undergoing cardiac or vascular surgery. In the pooled results from seven studies they report no statistically significant difference between the two groups in terms of mortality, length of stay or other outcomes. One limitation is the small difference in haemoglobin thresholds between the restrictive and liberal protocols studied, often a 10 g/L difference. The impact of this small difference is evident in the mean units of red cells transfused between groups, approximately half a unit, with patients in the liberal arm transfused a mean 1.9 red cell units and patients in the restrictive arm a mean of 1.4 units.

Docherty and colleagues also conducted a systematic review and meta-analysis looked at the effect of restrictive versus liberal transfusion strategies in patients with cardiovascular disease undergoing non-cardiac surgery. The main outcome investigated was 30-day mortality and cardiovascular events. The authors found no statistically significant difference in 30-day mortality between groups (risk ratio 1.15, 95% CI 0.88 to 1.50). However, there was a significant increased risk of acute coronary syndrome in patients assigned to a restrictive threshold when compared with patients assigned to a liberal transfusion threshold (risk ratio 1.78, 95% CI 1.18

to 2.70). As is common with other the other meta-analyses reviewed, one limitation of this review is the overlapping transfusion thresholds studied. Of the studies pooled the cut-off values for the restrictive transfusion thresholds ranged from 70 to 97 g/L, the cut-offs for the liberal transfusion thresholds ranged from 90 to 113 g/L.

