## 6.5. Sample size estimation.

Given the inclusion and exclusion criteria, there are expected to be between 60,000-70,000 consecutive inpatient admissions in the study cohort.

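### Comorbidity enters every model only as one Charlson-based score, whose fixed weights may leave residual confounding of unknown size in the transfusion estimate

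*Protocol*

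**What the plan says.** Section 6.2 of the protocol lists the adjusters: "Potential confounders collected will include age at admission, sex, hospital, discharge year, admission type (emergency or elective), clinical specialty, and patient comorbidities". It then gives the form that the last of these takes: "Patient comorbidities will be assigned a score based on the Charlson Comorbidity Index derived from ICD-10 codes for the comorbidities identified". A timing safeguard follows: "To ensure the Charlson score represents patient comorbidities on admission, hospital-acquired complications will be excluded from the calculation". Section 6.4 adds: "All regression models will adjust for the same potential confounders". The form of the comorbidity adjuster is therefore stated in the protocol and applies to every regression model.

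The protocol does not say whether the score is entered as a linear term or in groups. The further data items listed in section 6.2 include no flags for individual conditions. Section 6.5 says that "there are expected to be between 60,000-70,000 consecutive inpatient admissions in the study cohort".

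**The concern.** Section 6.3 rests the validity of the results partly on statistical adjustment, so the form of the comorbidity adjuster matters. Suppose the score is entered in a form that fits. It then removes confounding by comorbidity if death depends on the conditions only through the score, given the other covariates. It also does so if the decision to transfuse depends on them only through the score. Either condition is enough, but neither is assured. Two patients with the same score can have different diseases, with different chances of being transfused and of dying.

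Heart disease is the natural example. Section 5 reports, from a meta-analysis in patients with cardiovascular disease, that "there was a significant increased risk of acute coronary syndrome in patients assigned to a restrictive threshold" (risk ratio 1.78, 95% CI 1.18 to 2.70). That is some ground for not treating heart disease as interchangeable with any other condition of equal weight. If its links with transfusion and death depart from its weight, the remainder goes into the transfusion coefficient, which is the quantity sought in Objective 1.

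**Working it through.** The protocol gives no estimate of confounding, no prevalences and no condition-level associations, so there is no figure of its own to reproduce. The check asks how far a score-adjusted odds ratio can move from 1.00 when transfusion has no effect.

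**Inputs, all assumed.**
- Heart disease: weight 1, prevalence 8% or 15%.
- Kidney disease: weight 2, prevalence 8% or 12% in patients without heart disease, associated with heart disease at an odds ratio of 3. It serves only as an illustrative second condition.
- Six other independent conditions: weight 1 and prevalence 8% each.
- Patients with no condition: log odds of transfusion −1.8, so 1/(1 + e^1.8) = 14.2% are transfused; log odds of death −4.3, so 1/(1 + e^4.3) = 1.3% die.
- True transfusion odds ratio: 1.00.

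**Method.** Every combination of conditions, transfusion and death was enumerated with its exact probability, and logistic models were fitted to these probabilities (the large-sample limit). The models adjusted for nothing (crude), for a linear score, for the score in groups 0/1/2/3+, or for the conditions themselves.

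Share left = ln(score-adjusted OR) / ln(crude OR).

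**Results.** Condition odds ratios are given as heart / kidney / each other condition. Each range covers the two prevalence settings.

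| Scenario | ORs for transfusion | ORs for death | Crude OR | Linear score | Grouped score | Share left |
|---|---|---|---|---|---|---|
| Equal effects | 1.5/1.5/1.5 | 1.5/1.5/1.5 | 1.138–1.164 | 1.012–1.015 | 1.018–1.026 | 9–17% |
| Effects follow the weights | 1.5/2.25/1.5 | 1.5/2.25/1.5 | 1.223–1.288 | 1.000 | 1.012–1.020 | 0–8% |
| Heart, kidney modestly stronger | 1.6/2.0/1.3 | 2.0/2.0/1.4 | 1.173–1.243 | 1.008–1.011 | 1.017–1.026 | 5–12% |
| Heart, kidney strong, others weak | 2.0/2.5/1.1 | 3.0/2.5/1.2 | 1.312–1.468 | 1.094–1.107 | 1.097–1.116 | 27–34% |
| Heart, kidney extreme, others nil | 3.0/3.0/1.0 | 4.0/4.0/1.0 | 1.743–2.073 | 1.325–1.356 | 1.316–1.348 | 41–51% |

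Example, fourth row, lower prevalence, linear score: ln(1.094)/ln(1.312) = 0.0898/0.2716 = 33%.

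With the conditions entered separately, the odds ratio is 1.000 in every row. This follows by construction, because that model is the one that generated the data.

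The last row is a stress test: six of the eight conditions have no link with either transfusion or death. It is not carried into the range. The first four rows give 1.00 to 1.12.

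**Number of terms.** Assuming about 17 conditions in the index (the protocol gives no count), replacing one score term adds 17 − 1 = 16 parameters. In a variant calculation with 12 conditions, seven haemoglobin bands, 65,000 admissions, 7.5% transfused and 1.7% mortality (all assumed apart from the cohort size and the bands), using indicators in place of the score raised the standard error of the transfusion coefficient by about 1% or less.

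**The case against.** A Charlson score is a recognised adjuster, and the protocol does not rule out condition-level sensitivity analyses. An analysis plan that is not shown may contain them. This stands as a reason to treat the point as an improvement. It does not remove the point, because the protocol itself states the score as the form of adjustment.

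Four stronger readings are tempting, and the documents do not support them.

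- **That the score leaves much of the confounding.** A reader might infer this, but no figure in the protocol shows it. In three of the five scenarios the share left is 17% or less. The calculation also omits age, admission type and clinical specialty, all of which are planned adjusters. Cardiothoracic and vascular surgery are separate specialties in section 6.1 and may already carry part of the heart-disease effect.
- **That heart and kidney patients are known to be confounded here.** The meta-analysis cited in section 5 found no significant difference in 30-day mortality (risk ratio 1.15, 95% CI 0.88 to 1.50), which is one of this study's outcomes. It says nothing about who is transfused in these hospitals. The protocol does not link chronic kidney disease to the transfusion decision.
- **That the bias would imitate the effect modification asked about in Objective 2.** This needs a preference to transfuse certain patients that changes with haemoglobin. The protocol gives no such figures, and section 4 expects both transfused and untransfused patients at low levels. It is possible but not shown.
- **That separate indicators would restore an unbiased estimate.** The value of 1.00 above reflects only the assumed model. Neither a score nor yes/no flags record how severe a disease is.

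It is also fair to say that the change is not free. The flags must exist in order to build the score, but the listed data items do not include them, and under section 6.7 a separate data manager makes the extract.

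**Conclusion.** The point holds in a limited form. Sections 6.2 and 6.4 adjust for comorbidity only through one score with fixed relative weights, and this may leave residual confounding in the transfusion estimate. Its size is unknown. Under the assumed inputs the spurious odds ratio runs from about 1.00, when condition effects follow the weights, to about 1.12, when a few conditions have strong and selective effects. Allowing for age, specialty and admission type might change this, and the protocol offers nothing that narrows the range. The case for acting rests on the low cost of relaxing the fixed weights, not on a demonstrated large bias.

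**What to change.** In section 6.2, add the individual Charlson conditions to the data items, as yes/no flags with hospital-acquired complications excluded, as is already planned for the score. In section 6.4, state that these flags, with very rare conditions merged, replace the score as the comorbidity adjusters in the logistic, length-of-stay and Cox models. Keep the score to describe the cohort or for a sensitivity analysis.

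The cost is a short change to each section, about 16 more parameters and a negligible loss of precision in a cohort of 60,000 to 70,000 admissions. The protocol gives no death rate, so the number of rare conditions to merge should be settled once the counts are known, without reference to the transfusion results. The extract must carry the flags, and this is best arranged beforehand, because section 6.7 has the extraction code deleted six months after extraction. The report should say that disease severity remains unmeasured and that some confounding is therefore likely to persist.
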